**PI NAME: [name]**

**1. OBJECTIVES, SPECIFIC AIMS, BACKGROUND, AND SIGNIFICANCE**

**Background**

Intimate partner violence (IPV) is a major public health concern for perinatal women. The American College of Obstetricians and Gynecologists (ACOG) has defined IPV as violence by an intimate partner that may involve physical altercation (e.g., such as hitting, slapping or kicking), emotional or physical threats, and/or forced sexual relations. Prevalence rates of IPV prior to pregnancy (within the past year) range from 3% to 9% and for the postpartum period rates of physical IPV ranging from 3.2% to 7.4%; a rate that is in sharp contrast to the U.S. national average of 1.5% past-year prevalence for IPV among women. When emotional abuse is included, studies have found from 21% to 33% of perinatal women report IPV. Furthermore, perinatal women report commission as well as receipt of IPV, consistent with the larger literature that finds that the majority of IPV victims have comparable rates of perpetration behaviors. Bidirectional IPV can place women at high-risk for injury and revictimization.

*Negative effects of IPV during the perinatal period:* Although IPV at any time during a woman's life is devastating, a woman who experiences IPV during the perinatal period is at risk not only for her own health (e.g., anemia, maternal death, and poor mental health,) but also for the health of her developing fetus (e.g., preterm delivery, low birthweight (see reviews,) and the health of her infant (e.g., poor infant general health, difficult temperament, deficits in emotional regulation, eating and sleep disturbances, disturbed attachment relations). Based on this literature, researchers have suggested that exposure to IPV in infancy may be a key mechanism underlying the intergenerational transmission of IPV.

*High mental illness burden among perinatal women with IPV:* There is mounting evidence from epidemiological studies that IPV markedly increases the risk of several psychiatric disorders. In general, IPV is associated with mental health burdens among women, that includes depression, posttraumatic stress disorder (PTSD), low-self-esteem, suicidal thinking, and suicide attempts. Specific to postpartum women, research has found a strong association between IPV and postpartum depression. Although no studies, to date, have focused exclusively on rates of psychiatric disorders found among pregnant women with IPV, research on perinatal women has found IPV-positive women to have a significantly higher rate of a current mood or anxiety diagnosis. In general, research has found prevalence rates of lifetime physical IPV among women with mental health disorders that range from 50% and above up to an astounding 75%. Furthermore, women who report bidirectional IPV report more mental health problems than IPV victims alone.

*Screening and intervention of perinatal women at mental health clinics is important because:* 1) A robust relationship exists between IPV and psychiatric disorders; 2) The presence of IPV reduces the utilization of mental health care; 3) In our study in which we conducted a retrospective chart review of 299 perinatal women attending mental health treatment, perinatal women with current victimization were more than twice as likely to leave treatment than those without current violence in their lives; 4) IPV and untreated mental illness pose a dual threat of adverse health outcomes to a perinatal woman and her developing fetus/infant; 5) Untreated psychiatric disorders are associated with partner revictimization and can interfere with IPV victims' ability to effectively use important shelter and community resources necessary for establishing safety for themselves and their children; 6) At least 20% of perinatal women seeking mental health treatment report ongoing interpersonal violence at

intake; 7) Given the high rates of IPV among women who seek mental health treatment, mental health treatment settings compared to other medical settings (e.g. primary care) are more effective sites for focused case finding and interventions.

Despite the need, recent research suggests that there are low screening and intervention rates of female mental health patients with IPV by mental health providers psychiatrists hold less supportive attitudes towards IPV victims than other physicians, IPV training and knowledge of resources is limited among psychiatric residents, and mental health professionals find enquiry about domestic violence difficult because of their lack of knowledge and expertise in this area and/or because they do not think it is part of their role. As researchers have noted, there are much needed but inadequate systems in place for mental health clinics or providers to respond to women with IPV. Virtually no empirically-based interventions exist that address IPV among mental health treatment-seeking perinatal women. Women in the perinatal period were selected for two primary reasons: (a) interventions at this juncture may take advantage of a particularly salient point in a woman's life, in which she may be more open to considering behavior change; and (b) any positive change made has the possibility of a dual impact, on the woman's life as well as that of her infant. The proposed project will test an innovative, high-reach, easily implementable, low-cost computer-delivered intervention, Reach Out for a Safe Environment (ROSE), which is theoretically driven and addresses known barriers in early intervention with at-risk women throughout the perinatal period. Preliminary data from our pilot study provide reassurance that ROSE will successfully reduce IPV in our target population. A fully powered RCT trial of ROSE is necessary to determine efficacy. A cost estimate in a real-life clinical setting will provide information to facilitate implementation and dissemination.

The intervention (ROSE) will represent the first IPV risk reduction intervention for women, which is tailored to the specific needs of perinatal women with IPV within a mental health treatment setting. If the proposed intervention is found to be efficacious in our vulnerable target population, we anticipate that it could have significant implications for IPV prevention efforts for other childbearing victimized women seeking mental health treatment and victimized women, in general.

## Objectives

In our R21 preliminary work, we demonstrated the feasibility and acceptability of ROSE, a computerized intervention for perinatal women with recent IPV who seek mental health treatment. In our pilot work, there were high ratings of satisfaction for ROSE. 100% completed the computerized intervention; 93% participated in the booster and 92% in the 4-month follow up assessment. Further, participants in the ROSE condition demonstrated a significantly larger change in frequency of IPV from baseline to follow-up (4 months after intake) than participants in the control condition ( $p < 0.007$ ).

The goal of this proposed study is to build upon these promising preliminary findings by testing whether ROSE reduces the frequency of IPV in a larger sample of perinatal women seeking mental health treatment, compare the effects of ROSE to an attention, time, and information matched control condition in two real-life clinical settings, examine the effects of the intervention for a more extended period of time, and include a cost estimate of ROSE. To achieve this, we propose a two-group, randomized controlled trial in which 186 perinatal women seeking mental health treatment are assigned to either (a) a computer-delivered, single-session brief intervention plus one interventionist-led phone booster; (ROSE); or (b) a computer-delivered control + one interventionist-led phone booster condition. Computer-delivered follow-up assessments will occur at 6-weeks, 3 months, 6 months, and 12 months after the baseline assessment. More specifically, we propose the following Specific Aims:

### Aim 1 (Primary Outcome)

To test the hypothesis that ROSE, compared to an attention, time and information matched control condition, will be associated with a lower frequency of IPV among perinatal women seeking mental health treatment at 6-weeks, 3 months, 6 months, and 12 months follow up.

### Aim 2 (Secondary Outcomes)

- (a) ROSE, as compared to control, will result in greater positive affect and well-being at 6-weeks, 3, 6- and 12-months follow up;
- (b) ROSE, as compared to control, will result in greater perceived emotional support at 6-weeks, 3, 6- and 12-months follow up;
- (c) For future implementation and dissemination, we will estimate the resources needed and costs to deliver ROSE. Additionally, we will estimate the incremental cost effectiveness of ROSE compared with treatment as usual.

### **Aim 3 (Mediation)**

To examine the role of theorized mediators of empowerment and self-efficacy on the effect of SURE.

## **2. STUDY DESIGN, METHODS, AND PROCEDURES**

### **Study Design**

Women (18 to 45 years old) presenting for an intake appointment at The Center for Women's Behavioral Health (WBH) at Women and Infants Hospital (WIH) and at The Perinatal Psychiatry Clinic (PPC) at the University of Michigan Health System (UMHS) will be screened for IPV victimization. Women who are pregnant or within 12 months postpartum – and report past 12-month history of IPV will be invited to participate in the study. At each site, those providing informed consent will be randomized either to an attention, time and information matched control condition or ROSE arm. Participants in both conditions will receive a phone booster within 4-weeks of their baseline assessment. Follow up assessments consisting of validated questionnaires will occur at 6-weeks after baseline assessment, and 3-, 6-, and 12 months, which will capture both immediate and sustained change and allow us to capture trajectories of IPV change. The booster session will be audio recorded so that adherence and competence ratings of the booster sessions can be conducted. These digital recordings which will be labeled with the study identification number and the booster session date and will be transferred to Women and Infants Hospital secure computer server via a secure server access. Access to the audio recordings will be limited to research staff. See "Sources of Materials" section for the assessments to be collected at each time point. If participants do not want to be audio recorded, they can still participate in the study.

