#### Overview of study phases

#### Inclusion and Exclusion Criteria/ Study Population

The inclusion criteria of this study are being a woman 18 to 45 years old who presents for an intake appointment at The Center for Women's Behavioral Health (WBH) at Women and Infants Hospital (WIH). Women who are pregnant or within 12 months postpartum – and report past 12-month history of IPV will be invited to participate in the study. Other inclusion criteria are the ability to understand study procedures in English, and willingness to complete follow-up session.

Exclusion criteria include: 1) No access to a computer (PC, tablet, iPad, Mac) or Smartphone (a device with internet) and unwilling to come to the hospital to be consented and to view the intervention; 2) Reports discomfort with using the internet and unwilling to come to the hospital to be consented and to view the intervention; 3) Living with an abusive partner, at risk for severe injury or homicide as determined by the 5-item Danger Assessment, unwilling to create a private email and unwilling to come to the hospital, 4) Has a past or current abuser who is making the woman feel unsafe or she has no private email and unwilling to set up a temporary email or come to the hospital to be consented and to view the intervention, 5) Reports no privacy to view the consent form online and view a 40-minute online intervention on domestic violence and unwilling to come to the hospital to be consented and view the intervention. 6) Responds yes to any of the questions to determine if Spyware or Stalkerware is likely operating on her device and is unwilling to come to the hospital to be consented and view the intervention. Others include inability to provide informed consent (e.g., due to psychosis, intoxication, or other clear cognitive impairment) or inability to understand English (understand the consent form when read aloud and assessments that are narrated by computer). Perinatal transgender men will be excluded because transgender persons confront many IPV issues that are unique to them as a group.

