**Recruitment Methods and Informed Consent Process**

The clinical trial will be conducted at two sites. We will recruit perinatal women from The Center for Women's Behavioral Health (WBH) at Women and Infants Hospital (WIH) and from The Perinatal Psychiatry Clinic (PPC) within the University of Michigan Health System (UMHS). Participants will be 186 pregnant or postpartum women (up to 12 months after delivery), 18 to 45 years of age, who have received clinical services at WBH (i.e., initial assessment or treatment) within the last twelve months. We have included women who are up to 12 months postpartum, because there is general consensus in the literature that postpartum refers to 12 months after delivery [56]. In addition, the perinatal women will have endorsed any IPV during the past 12 months as measured by the Woman Abuse Screening Tool (WAST[57]). The WAST is an 8-item instrument that measures physical, sexual, and emotional abuse and is consistent with the definition of IPV as defined by The American College of Obstetricians and Gynecologists[1,57]. It has correctly classified 100% of nonabused women and 92% of abused women in a known-group analysis[57], has good internal reliability[58], and has adequate concurrent validity, even with ethnic minorities[58]. Consistent with similar studies, IPV status will be positive if a woman obtains a score of 4 or more on the WAST. Other inclusion criteria will be ability to understand study procedures in English, and willingness to complete follow-up session.

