Stalkerware is operating on the recruit's devices will be asked. To establish safety, women living with a current abusive partner will be asked about their risk for severe injury or homicide as determined by the 5-item Danger Assessment. If women meet criteria for severe injury or homicide risk or risk of spyware or Stalkerware, they will be given the option to come into the hospital to be consented and view the intervention,

[figure not shown]
As part of the phone or in-person consent those who qualify will be asked to share the information gained from the screener survey as part of the study data. Participants will be reminded that they are not required to participate in the study and that they will receive the standard care provided by WBH and Women and Infants Hospital regardless of whether or not they choose to participate.

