### **Sources of Materials**

The following assessment measures will be administered at the baseline assessment:

1. Demographic information, including age, race, ethnicity, marital/partner status, parity, employment, socioeconomic status.
2. Relationship information, such as current relationship to abuser/s, length of relationship/s, etc.

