#### Primary Outcome Measure:

At baseline *frequency of IPV* for the past 12 months will be measured using the Composite Abuse Scale (CAS[60]). The CAS assesses the frequency of psychological, physical, sexual, and combined severe violence for each intimate relationship over a specified period of time. The CAS has demonstrated face, content, criterion, and construct validity[61]. The scale as a whole and its 4 subscales have all demonstrated good internal consistency and reliability[61]. The instrument will be administered at baseline and at each follow-up interval.

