Participants who return to or continue to have contact with their abuser may be at increased risk for abuse if he or she were to find out about the woman's participation in the research project. The measures suggested by Sullivan and Cain (2004) will be taken to maximize participant safety throughout the research. The office research line is a number that is blocked and the line will be answered, "Women and Infants Program," and partner violence will never be mentioned. Likewise, staff work cell will be answered with Women and Infants Program. When potential participants are contacted through text or email using contact information obtained from EPIC, RAs will let potential participants know that they are from Women and Infants Hospital and that they will be calling them and provide their study cell number. If reference to the screener is made in text or email, it will be referred to as a brief women's health survey. Details of the research are not provided to anyone other than the actual participant. During each contact, participants will first be asked if it is a safe time to speak. Safe contact for follow-up assessments will be negotiated at each stage of the research. Both written and verbal contacts will be vague and never mention that the research involves partner violence. Safety plans will be negotiated up front (e.g., code words, cover story for reason for interview) if ever the abuser were to interrupt a phone call or assessment or –if during a call to the participant there is noise and concern for the safety of the participant, research staff will ask the participant if she is safe and ask if the police needs to be contacted. If participant says yes to police being contacted, the research staff will call the police. Any handouts with important information (e.g., hotline numbers) will be available in wallet size copies without any reference to the study or name of organization. Participants' safety contact information, including the Locator Form, will be updated and confirmed at each assessment to determine if the

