**Site Differences:** In the preliminary analyses, participants from the two sites will be compared on all demographic and background information. We will also check for site effects with each specific hypothesis by including site as a fixed effect factor in the analysis. Site main effects and, as appropriate, interactions of site with relevant factors will be included. If site differences (and the interactions) are non-significant, this factor will be removed. Including site as a fixed effect and assuming an equal distribution of participants between sites and by treatment within each site will not change the overall sample size needed. However, the study may lack power to detect a site-by-treatment interaction unless the difference is large. Powering the study to detect the expected treatment effect separately by site is not feasible and would elevate the site-effect to a higher aim as opposed to being a check on the analysis[77].

**Aim 1:** For hypothesis 1 (primary outcome), the outcome (frequency of IPV) will be analyzed under a clustered count regression framework (Poisson or Negative Binomial) with frequency as outcome, and time (6-weeks, 3-, 6- and 12 months,), group (ROSE, control) and time-by-group interaction, with the

baseline (BL) IPV frequency as the primary covariate. A generalized linear mixed models (GLIMMIX) approach will be adopted by means of a random subject intercept to account for the clustering within each participant. Changes over time within each group will be estimated post-hoc by sliced effects derived from the regression model with adjustment for multiple comparisons. In additional analysis, reduction in proportion of participants experiencing a binary outcome of  $IPV \geq 1$  days within the 90-day period will be analyzed using a clustered logistic regression with a dichotomous outcome, again with BL IPV frequency as a covariate.

**Aim 2:** Similar analyses will be conducted for the secondary outcomes of positive affect and well-being and for perceived emotional support (Aim 2a and 2b). For cost estimation (Aim 2c) see below.

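### Baseline relationship to the abuser is collected but not prespecified in the Aim 1 model; adding it is a nearly free gain in precision, not a correction to the sample size

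*Combined protocol and SAP*

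**What the plan says.** Entry rests on the previous year: women who are pregnant or up to 12 months postpartum and "report past 12-month history of IPV will be invited to participate in the study" (Study Design). Recruitment Methods and Informed Consent Process makes this operational: "IPV status will be positive if a woman obtains a score of 4 or more on the WAST". No section requires a current relationship or current contact with the abuser.

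The safety provisions distinguish the groups. One exclusion criterion, conditional on email and travel arrangements, concerns a woman who "Has a past or current abuser who is making the woman feel unsafe". At consent, "women living with a current abusive partner will be asked about their risk for severe injury or homicide", so women living with the abuser are a subset of recruits. Protection against risk adds, about study-related violence: "Participants who return to or continue to have contact with their abuser may be at increased risk for abuse".

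At baseline, IPV frequency "for the past 12 months will be measured using the Composite Abuse Scale" (Primary Outcome Measure). At follow-up, Protection against risk describes the CAS as covering the time since the previous assessment. Sources of Materials lists among the baseline items: "Relationship information, such as current relationship to abuser/s, length of relationship/s, etc".

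The Aim 1 count model contains time, group, their interaction and "baseline (BL) IPV frequency as the primary covariate"; site is a conditional fixed effect. Under Data Analysis, IPV relationship variables are compared between arms, and any with p ≤ 0.05 join the main analyses.

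**The concern.** A 12-month total looks back, while the primary outcome looks forward from randomisation. As an illustration with an assumed constant monthly rate, a woman who left nine months ago after 3 months at 4 units a month and a woman still in the relationship at 1 unit a month both total 12 over the year (3 × 4 = 12 × 1). Their expected abuse over the next 6 weeks to 12 months may differ a great deal. If so, relationship status predicts the outcome beyond baseline CAS, and leaving it out keeps that variation in the between-woman error.

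The Data Analysis rule does not supply the missing term. It admits a variable because the arms differ on it by chance, not because it predicts the outcome. Under sound randomisation a single variable passes at p ≤ 0.05 about 5% of the time. At stake is precision of the ROSE effect that could be recovered from data the trial will already hold.

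**Working it through.** **1. Reproduce the plan's sample size.** Inputs from the Power paragraph: d = 0.4, SD 20 (a difference of 8 CAS points), four follow-ups, within-subject correlation 0.62, 80% power, 5% level (two-sided assumed).

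- Variance factor for a woman's mean of four follow-ups: [1 + 3 × 0.62]/4 = 0.715.
- n per group = 2(1.96 + 0.8416)²/0.4² × 0.715 = 98.11 × 0.715 = 70.1, so 71. The t-based version gives 72, against 74 stated.
- Power at 74 per group: 82.1% (normal) or 81.6% (t).
- Dropout: 74/0.80 = 92.5, so 93 per arm, as stated.

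The figure is reproduced closely, and without any baseline term.

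**2. Where a baseline predictor can act.** Of the 0.715, the between-woman part is 0.62, or 0.62/0.715 = 87%. More follow-ups do not reduce that part; a prognostic baseline covariate can.

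**3. Effect on the plan's own calculation.** Let R² be the share of the variance of the four-visit mean that status explains. The documents give no value, so a range is assumed. SE = 20 × √(0.715 × (1 − R²) × 2/74).

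| R² (assumed) | SE, CAS points | Power at 74 per group | n per group for 80% |
|---|---|---|---|
| 0 | 2.78 | 82.1% | 71 |
| 0.05 | 2.71 | 83.9% | 67 |
| 0.10 | 2.64 | 85.8% | 64 |
| 0.20 | 2.49 | 89.6% | 57 |
| 0.30 | 2.33 | 93.0% | 50 |

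The Aim 1 model also adjusts for baseline CAS, so the starting point is higher. The factor becomes 0.715 − r², with r the assumed correlation of baseline with follow-up CAS. At r = 0.3, power is 86.8% and rises to 90.0% (R² 0.10) or 93.1% (R² 0.20), with R² now the share of the variance left after baseline adjustment. At r = 0.62 it is 98.8% and rises to 99.4% or 99.7%.

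**4. How large the gain might be in a count model.** Simulation with 74 per group and the mean of four follow-ups, using a log-link Poisson working model with robust SE, adjusted for log(1 + baseline CAS), 600 runs per cell. All parameters are assumed, and baseline CAS is generated independently of status, which favours the extra term. Entries are the reduction in variance of the arm log rate ratio when status is added.

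| Follow-up abuse in ended relationships, relative to others | 20% ended | 40% ended | 60% ended |
|---|---|---|---|
| 100% | 0.3% | −1.5% | −0.9% |
| 70% | 2.3% | 3.6% | 2.8% |
| 50% | 5.2% | 5.4% | 10.7% |
| 30% | 11.3% | 20.2% | 28.9% |
| 10% | 16.5% | 27.0% | 35.4% |

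The first row is nil apart from simulation noise. These are linear and working-model approximations to the planned Poisson or negative binomial mixed model.

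**The case against.** **Baseline CAS may already track status.** The scale is scored for each intimate relationship over a period. A woman who left nine months ago had about 3 of 12 months of exposure in that relationship and will tend to score lower. A further simulation, with other assumed parameters, shows that this matters. At half the follow-up abuse, the variance reduction was 14% to 30% with baseline CAS independent of status, but 2% to 4% when baseline CAS reflected the shorter exposure. At one fifth of the abuse, the figures were 36% to 61% and 14% to 42%. So it is too strong to say that baseline CAS cannot tell the groups apart; it probably does so poorly. This objection reduces the gain but removes it only where status adds nothing.

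**An ended relationship need not mean little abuse.** The exclusion criteria recognise past abusers who still make a woman feel unsafe, Protection against risk speaks of returning to or staying in contact with the abuser, and CAS also counts new partners. No document gives the share of ended relationships or their follow-up scores. This stands.

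**A reader might infer that the trial is underpowered.** The documents do not support that. The SD and correlation come from a pilot in perinatal women with recent IPV seeking mental health treatment, so the mix may already be in the SD of 20. The 74 per group also does not rely on covariate adjustment.

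**The plan has a route for relationship variables.** It does, but the route selects on imbalance, so it rarely delivers the term.

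**Conclusion.** The point holds as an efficiency improvement. Entry allows the mix, the named covariate probably reflects it only in part, and a variable that addresses it directly is collected but not prespecified.

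The size rests on two unknowns: the share of women with ended relationships (20% to 60% assumed) and how far their follow-up abuse differs given baseline CAS. The variance reduction is about nil if status is not prognostic, a few percent to about 10% at half the abuse, and up to about a third if abuse is far lower. These are the ends of an assumed range, not bounds.

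Three stronger conclusions should not be drawn. The planned 80% power is not shown to be missed. The primary comparison is not biased by omitting the term, because status at baseline precedes randomisation. Nor is every effect estimate unaffected by adding it: the rate ratio from the log-link count model keeps its meaning, but an odds ratio generally changes when a prognostic covariate is added, and this concerns the additional binary analysis.

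**What to change.** In the Aim 1 count model, prespecify a fixed effect for baseline relationship status (current versus ended), taken from the item under Sources of Materials. Include it alongside baseline CAS whatever the between-arm test shows.

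Define the variable in the SAP before outcome data are seen. The item allows for several abusers and several relationships, and the documents show no response categories. The definition therefore needs a rule for women with more than one abuser and a rule for ended relationships with continuing contact.

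If the term is also used in the additional logistic analysis, state that the odds ratio is then conditional on relationship status.

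The cost is one degree of freedom and a short SAP definition. No new data, no change to eligibility and no change to the sample size are needed. If status proves not to be prognostic, almost nothing is lost.
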